¹ COPD exacerbation is defined as an acute event characterized by aggravation of the event within 2-3 or more days. Exacerbation manifests in intensification of respiratory disorders beyond their regular daily fluctuations and require administration of products in addition to the previously prescribed basic therapy as well as a rescue drug for symptom relief (salbutamol). Additional products include antibacterial drugs, systemic corticosteroids and/or emergency therapy (ambulance call) or hospitalization for COPD exacerbation.

COPD exacerbation is recorded as an adverse event. If a COPD exacerbation develops within the first week of the subject participation in the study, it will not be considered as a secondary inefficacy criterion.

 Frequency of cough and other respiratory patterns according to 24-hour daily monitoring (using WHolterTM) after 4 weeks of the treatment compared to baseline.

Safety assessment

- Adverse events (AEs) during the treatment, AEs severity and relations to the study drug, and AEs outcomes.
- Changes in vital signs.

Study design

Study design: multicenter, double-blind, randomized, parallel group placebo-controlled study.

The study will enroll men and women (aged 40 to 80 years) with cough associated with stable $COPD^2$. Subjects with COPD diagnosed more than 12 months earlier obtaining allowed basic therapy³ and retaining cough ≥ 2 points (according to Cough Severity Scale [CSS]) despite their therapy should be considered as the study candidates.

After signing patient information sheet (informed consent form) to participate in the clinical trial, medical history and objective examination are performed, cough severity is assessed (using TCSS; at baseline evaluation of diurnal and nocturnal cough the number of episodes and cough severity in the preceding day is taken into account) as well as intensity of COPD effect on the subject (CAT test), concomitant therapy is recorded, computer spirometry with evaluation of baseline FEV₁/FVC and post-bronchodilator FEV₁ (where respiratory function cannot be assessed, the results of the previous examination dating no more than 3 months earlier may be used). Females of childbearing potential will undergo pregnancy test.

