- 24. Patient is a study specialist of the centre and directly involved in the study, or is an immediate family member of the Investigator. Spouses, parents, children, or siblings, regardless of whether they are siblings or adopted are considered immediate family members.
- 25. The patients work for OOO "NPF "Materia Medica Holding", i.e. they are employees of the Company, temporary employees on a contract basis or appointed officials responsible for conduction of the study or their immediate family members.

Criteria for Withdrawal or Termination

- 1. COPD exacerbation.
- 2. The patient's inability or refusal to follow the protocol requirements.
- 3. The necessity to use medications prohibited within this trial.

- 4. Change in the stereotype of smoking (ceasing smoking for smokers, starting smoking for non-smokers).
- 5. An adverse event requiring discontinuation of the study drug.
- 6. Patients wish to complete the study ahead of schedule due to lack of treatment efficacy or for any other reason.
- 7. Cases not specified by the protocol when, according to the investigator's opinion, further participation in the study harms the patient.
- 8. Incorrect inclusion of ineligible patient.
- 9. Patient failed screening procedure.

Number of subjects

At least 238 patients will be enrolled, which is expected to yield at least 190 patients (95 x 2 groups (Rengalin and Placebo) completing all protocol procedures.

Interim analysis

An interim statistical analysis is not scheduled within the study.

Treatment

Group 1

Name of the medicinal product: Rengalin

Active ingredient: affinity purified antibodies to bradykinin -0.006 g*, affinity purified antibodies to histamine -0.066 g*, affinity purified antibodies to morphine -0.066 g*

* *Mixture of water-ethanol dilutions* 100^{12} , 100^{30} , 100^{50} of active substance used for saturation of isomalt.

Excipients: isomalt 0.506 g, microcrystalline cellulose 0,0275 g, magnesium stearate 0.0055 g, anhydrous citric acid 0.005225 g, colloidal anhydrous silica 0.00275 g, sodium cyclamate 0.00275 g, sodium saccharin 0.000275 g.

Method of administration: Tablet for oral use. Two tablets per intake. The tablet should be held in the mouth until complete dissolution. 2 tablets 3 times a day without food (i.e. 15-30 min prior to meal or 15-30 min after meal).

Dosage form: Tablets.

Description: White to off-white, round, flat, cylinder-shaped, beveled edge tablets scored on one side, with integral edges.

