Body weight measurement	+	
Measurement of body length/height	+	

	17-Oct-2016	
Procedure/day	Visit 1 (Day 1)	Visit 2 (Week 4±3 days)
Body mass index calculation	+	
Evaluation of cough severity (according to Cough Severity Scale)	+	+
Evaluation of COPD impact on the subject's life (CAT)	+	+
Pregnancy test	+	
Concomitant therapy	+	+
Computer spirometry* (evaluation of FEV1/FVC and post-bronchodilator FEV1)	+	
Eligibility assessment	+	
Randomization and prescription of study drug	+	
Study drug supply	+	
Study drug accountability, compliance assessment		+
Evaluation of treatment safety	+	+
24-hour cough monitoring**	+ **	+ **

* Where spirometry cannot be performed, spirometry parameters dating no more than 3 months will be recorded in CRF results. ** Performed in Institute of Pulmonology, EMPA of Pussia

** Performed in Institute of Pulmonology, FMBA of Russia.

Statistical Analyses.

Samples

Total set: all patients included in the study who have signed Informed Consent Form for participation in the study. All AEs including those occurred prior to the study therapy will be considered throughout the study for this sample.

Safety population: all patients who received at least one dose of the study drug. This sample will be used to *analyze the study treatment safety and tolerability*, since all the AEs identified after the study drug administration will be recorded.

Full Analysis Set. This sample includes all enrolled and randomized patients, except for those who met at least one of the following criteria:

- 1) non-compliance with inclusion / exclusion criteria;
- 2) the patient has not taken as minimum a single dose of the study drug;
- 3) lack of any data of the patient following randomization;

This sample is the most consistent with the "Intention-to-treat" principle, will be used for the *Intention-to-treat analysis (ITT analysis) of the the study therapy efficacy*.

Per protocol set. This sample includes all patients who completed the therapy as per the study protocol without any missing visits or significant protocol deviations. This sample will be used for the *Per Protocol analysis (PP- analysis) of the the study therapy efficacy*.

Mean value of the total set for the relevant day will be used to fill lacking/missing data.

Data treatment and all statistical calculations under the protocol will be made using SAS-9.4 statistical software⁴.

Evaluation of sample size

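### Neither the FAS nor the PP set is named primary, and the only missing-data rule, a mean pooled over both arms, can turn patients withdrawn for treatment failure into responders

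*Combined protocol and SAP*

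**What the plan says.** The primary endpoint (Endpoints) is binary: a fall in TCSS of at least 1 point from baseline after 4 weeks. The schedule of procedures has two visits, Day 1 and Week 4, so Week 4 is the only scheduled post-baseline TCSS.

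Under Statistical Analyses, Samples:

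- The total set is "all patients included in the study who have signed Informed Consent Form for participation in the study".
- The FAS is assigned to the intention-to-treat analysis of efficacy. It drops ineligible patients, patients who took no dose, and those with "lack of any data of the patient following randomization" (exclusion 3).
- The PP set is assigned to a second efficacy analysis: "This sample includes all patients who completed the therapy as per the study protocol without any missing visits or significant protocol deviations".
- Missing values have one rule: "Mean value of the total set for the relevant day will be used to fill lacking/missing data".

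The text calls the FAS the set closest to intention to treat, but ranks neither set. Evaluation of sample size (1.8) is built on per-protocol completers: 95 per group, raised to 238 for 20% withdrawal.

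Criteria for Withdrawal or Termination include COPD exacerbation (item 1) and "Patients wish to complete the study ahead of schedule due to lack of treatment efficacy or for any other reason" (item 6). Footnote 1 to the endpoints adds that "COPD exacerbation is recorded as an adverse event", and says of a first-week exacerbation that "it will not be considered as a secondary inefficacy criterion". Nothing says how a withdrawn patient is classified on the primary endpoint, and no sensitivity analysis is described.

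**The concern.** There are two gaps.

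First, if the FAS and PP results disagree, the plan does not say which one supports the superiority claim. The FAS label points one way and the sample-size basis points the other.

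Second, the fill is blind to arm and to reason for withdrawal, and it feeds a yes/no endpoint. A patient withdrawn for an exacerbation has an adverse event on record, so exclusion 3 does not remove that patient from the FAS, and a missing Week 4 score is filled. The same patient can then fail secondary endpoint 4 (no exacerbation) and still be a responder on the primary endpoint.

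If such withdrawals differ between arms, the false credit moves the treatment difference. It favours Rengalin when more Rengalin patients fail, and hides benefit when more placebo patients fail.

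**Working it through.** **1. The plan's own figures.** From Evaluation of sample size: two-sided 5%, 80% power, difference 0.2, equal groups. The response rates are not stated. The plan takes the worst case for this difference, which is 0.6 versus 0.4.

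- n per group = (1.960 + 0.842)² / 0.2² × (0.24 + 0.24) = 94.2, planned as 95.
- Total = 190 / 0.8 = 237.5, planned as 238 (119 per group).

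Both reproduce. The sample-size arithmetic is not in dispute.

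**2. If the TCSS is filled.** Let m be the pooled Week 4 mean. A filled patient responds when baseline − m ≥ 1, so only baseline matters. Assumed means (the documents give none):

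| Assumed m | Filled patients who become responders |
|---|---|
| 2.0 | all with baseline ≥ 3, none below |
| 3.0 | all with baseline ≥ 4, none below |
| 4.0 | all with baseline ≥ 5, none below |

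**3. If the response indicator is filled.** At 57/95 and 38/95 the pooled mean is (57 + 38)/190 = 0.50. Each filled patient becomes half a responder, which is not a count that the 2×2 test under Non-parametric criteria can use.

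**4. Effect on the difference.** Completers are 57/95 versus 38/95. The failure withdrawals kept in the FAS are assumed numbers.

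| Withdrawals, Rengalin v placebo | All non-responders | Half credited | All credited |
|---|---|---|---|
| 16 v 8 | 57/111 − 38/103 = 0.145 | 65/111 − 42/103 = 0.178 | 73/111 − 46/103 = 0.211 |
| 8 v 16 | 57/103 − 38/111 = 0.211 | 61/103 − 46/111 = 0.178 | 65/103 − 54/111 = 0.145 |
| 12 v 12 | 57/107 − 38/107 = 0.178 | 0.178 | 0.178 |

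**5. Can the conclusion change?** In every cell above the uncorrected chi-square p lies between 0.002 and 0.033, so significance is not lost. With a smaller completer effect, 55/95 versus 42/95, it can be gained or lost:

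- 16 v 8, non-responders: 55/111 v 42/103, difference 0.088, p = 0.20.
- 16 v 8, all credited: 71/111 v 50/103, difference 0.154, p = 0.023.
- 8 v 16, non-responders: 55/103 v 42/111, difference 0.156, p = 0.022.
- 8 v 16, all credited: 63/103 v 58/111, difference 0.089, p = 0.19.

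**6. Power of the FAS under a non-responder rule (secondary).** Completers stay at 0.6 versus 0.4 of 95 per arm, and w withdrawn patients per arm are added as non-responders. The rates are 57/(95 + w) and 38/(95 + w). Ranges cover the unpooled and pooled normal approximations and exact calculation.

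| w per arm | Power |
|---|---|
| 0 | 79–80% |
| 6 | 77–79% |
| 12 | 74–76% |
| 24 (119 − 95) | 71–74% |

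If the 0.2 difference instead held in all 119 per arm, power would be 87–88% (exact 86.5%).

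**The case against.** - **No harm at the planned effect.** In all the scenarios at 57/95 versus 38/95 the test still rejects, and equal failure withdrawals leave the difference unchanged. This is true. The bias needs unequal failure withdrawals, and a changed conclusion also needs a completer effect below the planned one; step 5 gives such cases.
- **Uncertain reach.** A patient who leaves for lack of efficacy may have no post-randomisation data and drop out under exclusion 3. If that exclusion means efficacy data only, almost nobody would be filled. This stands as a limit: the sure route into the FAS is for patients with some post-randomisation record, such as an exacerbation logged as an adverse event. Yet where exclusion 3 does apply, it removes from the FAS a patient whose treatment failed, which is no better.
- **Summary document.** The public text calls itself a protocol summary, so a fuller plan might rank the sets or describe an assessment at early termination. That is possible, and it softens the point about the primary set. The mean-fill rule, however, is stated outright.
- **The indicator reading is unlikely.** A mean for a given day more naturally describes a score. Agreed; the TCSS reading carries the argument.
- **Exacerbation is not cough failure.** It is a separate secondary endpoint, and the first-week exception treats early events leniently. A non-responder rule is therefore a choice, and it also fails patients who leave for unrelated reasons such as a change in smoking (item 4). This stands, and it is why a sensitivity analysis is needed.

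**Conclusion.** The concern holds. The public text names no primary analysis set, and its single missing-data rule can credit a response to a patient who left because treatment failed.

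With 16 versus 8 such patients, the choice between no credit and full credit moves the difference by 0.066 (0.145 to 0.211), against a planned effect of 0.2. With a smaller completer effect it can carry p across 0.05 in either direction.

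The size rests on assumed withdrawal splits, response rates and Week 4 means, because the documents give none, and on those patients being kept in the FAS. The direction of bias is not known in advance. The PP set excludes missing visits, so the fill matters mainly in the FAS. The defect is bias and an undefined primary result; it is not an error in the sample size. It should be corrected before unblinding.

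**What to change.** 1. Name the FAS as the primary set for the superiority claim and PP as supportive.
2. For the primary responder endpoint, keep FAS exclusions 1 and 2. Replace exclusion 3 and the total-set mean with one rule: an eligible, dosed patient without a Week 4 TCSS stays in the FAS and counts as a non-responder. State that the first-week exacerbation exception concerns the secondary criterion only.
3. Add one sensitivity analysis: multiple imputation of Week 4 TCSS by arm from baseline TCSS, with withdrawals for exacerbation or lack of efficacy kept as non-responders.
4. In Evaluation of sample size, state that 80% refers to 95 per-protocol completers per arm at 0.6 versus 0.4, and give FAS power as conditional on the number of withdrawn patients (step 6).
5. Clarify that 238 (119 per group) means patients randomised. The sample-size text counts signed consents, while the withdrawal criteria include "Patient failed screening procedure" (item 9).

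**Cost.** Wording in the protocol and SAP and one extra analysis. Some additional screening may be needed to randomise 238; the documents give no screen-failure rate. The non-responder rule does not raise power: it dilutes the difference, keeps more withdrawn patients in the set, and counts unrelated withdrawals as failures. If the sponsor wants 80% power in the FAS even with all 20% missing, about 136–147 per arm would be needed, depending on method (144 unpooled, 146 pooled, 147 exact, 136 exact with the number of withdrawals fixed).

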Multicenter Double-Blind Placebo-Controlled Parallel-Group Randomized Clinical Trial of Efficacy and Safety of Rengalin in the Treatment of Cough in Patients with Chronic Obstructive Pulmonary Disease

Phase IV

Sponsor

OOO «NPF «MATERIA MEDICA HOLDING»

Protocol numberMMH-RN-005Version date:October 17, 2016ClinicalTrials.gov Id:NCT03159091

Protocol Summary

This document represents the protocol summary for the study on human subjects. The study will be carried out in accordance with ICH GCP, National Standard of the Russian Federation GOST 52379-2005 "Good Clinical Practice", Helsinki Declaration of World Medical Association, relevant requirements of the regulatory authorities as well as the study procedures.

Title of Study

Multicenter double-blind placebo-controlled parallel-group randomized clinical trial of efficacy and safety of Rengalin in the treatment of Cough in patients with chronic obstructive pulmonary disease.

Phase: IV

Sponsor: OOO "NPF "Materia Medica Holding", Moscow, Russia *Protocol No.* MMH-RN-005

Objective of the study

• To obtain additional data on the efficacy and safety of Rengalin in the treatment of cough in patients with stable chronic obstructive pulmonary disease (COPD).

Endpoints

Primary endpoint

 Percentage of patients with a positive response after 4 weeks of the treatment (response criterion is the reducing of the Total Cough Severity Score (TCSS)* by ≥1 compared to baseline).

* according to the 12-point of the Cough Severity Scale.

Secondary endpoints

- 1. Severity of cough (TCSS according to the Cough Severity Scale) after 4 weeks of the treatment compared to baseline.
- Percentage of patients with ≥50% lesser cough severity (according to TCSS) after 4 weeks of the treatment.
- 3. The severity of the clinical symptoms of COPD (according to COPD Assessment Test [CAT]) after 4 weeks of the treatment.
- 4. Percentage of patients with no exacerbation of COPD¹ within 4 weeks of the treatment.

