Therefore, sample size will be **95** patients in each group (Rengalin and Placebo) to estimate superiority of the study drug over placebo.

Given potential withdrawal of at least 20% subjects during the study for various reasons, at least 238 subjects will be required to sign informed consent (119 per group).

Statistical criteria

All statistical calculations will be performed using two groups of statistical criteria:

- parametric to evaluate continuous and interval random variables;
- non-parametric for:
 - assessments of equality / inequality in the proportion of patients when compared for different visits,
 - analysis of frequencies of the compared variables,
 - assessment of continuous and interval random variables in case of violation of the normality assumption.

Parametric criteria

The application of parametric criteria will be accompanied by a check for normality of the compared samples (Kolmogorov-Smirnov test).

The following parametric methods and approaches are to be used:

• To assess the differences of continuous variables obtained in two different (independent) groups – Student t-test for independent samples.

⁵ The highest potential sample size at this effect size.

- To assess the dynamics of the compared indicators analysis of variance (ANOVA) or covariance (ANCOVA) in the modification with repeated measures.
- In case of multiple comparisons between the groups will apply a variety of corrections for multiplicity Dunnett, Tukey, Scheffe, Holm adaptive test, etc.
- In case of abnormal data distribution, approaches with the Generalized Linear Models and / or Mixed Linear Models will be used.
- Selection of the type of distribution, clarification of the factor and covariance structures of the model is carried out with fit statistics such as AIC (Akaike information criterion).

To perform the above-mentioned statistical tests and techniques, it is assumed that the following SAS procedures are used:

- UNIVARIATE check for normality of the compared distributions;
- CORR, MEANS calculation of descriptive statistics;
- TTEST Student t-test with all the modifications;
- GLM analysis of Generalized Linear Models for studying temporal dynamics (ANOVA, ANCOVA);
- GENMOD analysis of Generalized Linear Models.
- MIXED analysis of Generalized Linear Models.

Non-parametric criteria

Below, there are the main types of possible comparisons with the respective criteria:

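### Secondary endpoints 1 (TCSS) and 3 (CAT): no between-arm analysis is assigned and no baseline covariate is named; fixing baseline-adjusted ANCOVA would be a free gain in precision

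*Combined protocol and SAP*

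**What the plan says.** Secondary endpoint 1 is "Severity of cough (TCSS according to the Cough Severity Scale) after 4 weeks of the treatment compared to baseline". Secondary endpoint 3 is "The severity of the clinical symptoms of COPD (according to COPD Assessment Test [CAT]) after 4 weeks of the treatment", with no reference to baseline. The schedule of study procedures records both scores at Visit 1 (Day 1) and Visit 2 (Week 4), so each patient has one baseline and one outcome value.

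The Statistical criteria section lists methods by type of data and does not link them to endpoints:

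- Parametric, two groups: "To assess the differences of continuous variables obtained in two different (independent) groups", the plan names the "Student t-test for independent samples". It does not say whether the test is on the Week 4 score or on change.
- Parametric, change over time: "To assess the dynamics of the compared indicators analysis of variance (ANOVA) or covariance (ANCOVA) in the modification with repeated measures". The choice between the two is left open and no covariate is named.
- If the data are not normal, two routes are given without ranking. One is the non-parametric group, which covers "assessment of continuous and interval random variables in case of violation of the normality assumption"; the Mann-Whitney test is in its list of SAS procedures. The other is generalized linear and/or mixed models, with their form guided by fit statistics such as AIC.

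**The concern.** The baseline score is the obvious covariate for a Week 4 score, and it is already collected. The plan does not commit to using it. The t-test, if run on Week 4 scores, ignores baseline. If run on change, it subtracts the whole baseline value, whatever the correlation between visits. Repeated-measures ANOVA does not help: with only two visits, its group-by-visit term is the same test as the t-test on change.

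Two things are at stake. The first is precision: the interval for the Rengalin-placebo difference may be wider than the collected data allow. The second is that several tests remain possible for each endpoint. Each may hold its 5% level alone, but that does not protect a choice made after the results are known.

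**Working it through.** **1. The plan's own figure.** The stated formula at proportions 0.6 and 0.4, the pair that maximises the variance for a difference of 0.2, gives (1.960 + 0.842)² / 0.2² × (0.6×0.4 + 0.4×0.6) = 94.19, rounded up to 95 per group. Then 95/0.8 = 118.75, rounded up to 119 per group, or 238 in total. The figure reproduces. It belongs to the binary primary endpoint and is not affected by this point.

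**2. Variance formulas.** Let ρ be the correlation between baseline and Week 4, with a common SD σ. The per-arm variance factors are:

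- Week 4 t-test: σ²
- change t-test: 2σ²(1−ρ)
- ANCOVA: σ²(1−ρ²)

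The ratio of ANCOVA to the Week 4 t-test is therefore 1−ρ². The ratio to the change t-test is (1−ρ²)/[2(1−ρ)] = (1+ρ)/2. The documents give no ρ, so 0.3 to 0.7 is an assumption. These ratios apply to TCSS and CAT alike. At 95 per arm, the difference detectable with 80% power is 2.802 × √(2/95) = 0.406 SD for the Week 4 t-test. The other two scale by the square root of their variance factor.

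| Assumed ρ | 0.3 | 0.5 | 0.7 |
|---|---|---|---|
| ANCOVA variance / Week 4 t-test | 0.91 | 0.75 | 0.51 |
| ANCOVA variance / change t-test | 0.65 | 0.75 | 0.85 |
| Detectable difference, Week 4 t-test (SD units) | 0.406 | 0.406 | 0.406 |
| Detectable difference, change t-test | 0.481 | 0.406 | 0.315 |
| Detectable difference, ANCOVA | 0.388 | 0.352 | 0.290 |

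Against the better t-test in each column, the interval has √0.91 = 0.95, √0.75 = 0.87 and √0.85 = 0.92 of the width.

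**3. Simulation for TCSS.** From the documents: 95 per arm, a scale maximum of 12 and entry at TCSS 2 or more. Assumed: whole-number scores, an average fall of 1 point, a true difference of 0.7, latent baseline mean 6, SD 1.5 to 2.5. Baseline is kept within 2-12 and Week 4 clipped to 0-12, with 10,000 trials per setting. Power at SD 2:

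| Assumed ρ | 0.3 | 0.5 | 0.7 |
|---|---|---|---|
| ANCOVA | 70% | 78% | 90% |
| Week 4 t-test | 66% | 67% | 68% |
| Change t-test | 53% | 67% | 85% |
| Gain over the better t-test (points) | 3.8 | 11.2 | 5.1 |

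The gain is 2.6/5.6/1.5 points at SD 1.5 and 2.8/9.0/6.6 at SD 2.5. Rounding and the entry limit lower the realised correlation, so the simulated variance ratios against the Week 4 t-test (0.92-0.93/0.78-0.81/0.55-0.58) are a little less favourable than the formula.

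**4. Lower baseline.** Entry needs only TCSS 2 or more, so a mean of 6 may be too high. With latent mean 3 and SD 2, the ratio to the Week 4 t-test is about 0.96/0.85/0.66-0.68, and the gain over the better t-test is about 2/7/5 points. Over the whole assumed range the gain is about 1 to 11 points.

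**5. Mean-filled data.** With 119 per arm, 20% of Week 4 values missing at random and filled with the pooled Week 4 mean (baseline mean 6, SD 2), power is 69/75/86% for ANCOVA, 66/67/68% for the Week 4 t-test and 46/56/73% for the change t-test. The gain over the better t-test is then 69−66 = 3, 75−67 = 8 and 86−73 = 13 points. The fill shrinks the estimated difference from about 0.70 to 0.56 for all three tests, which is a separate issue.

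**6. Open choice.** With no true difference, each test alone rejects in about 5% of trials. Taking the smaller p-value of the Week 4 and change t-tests rejects in about 8.0-9.6%.

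**The case against.** Several objections have force.

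- *The t-test is not the only two-group test named.* A reader might infer that it is. The list of SAS procedures includes the Mann-Whitney test, and ANCOVA, generalized and mixed models also appear. What stands is narrower: the t-test is the only parametric method expressly assigned to two independent groups, and no listed method is tied to these endpoints or to a baseline covariate.
- *The largest gains come from the least applicable comparator.* At correlation 0.7, 95 per arm with ANCOVA matches 163-174 per arm with a Week 4 t-test. It is tempting to lead with that figure. But endpoint 1 is defined relative to baseline, which points to change, and there the match is 110-112 per arm. The gain over the better t-test is the fair measure.
- *The inputs are assumed.* This is correct. The documents give no mean, SD, correlation or continuous effect, and CAT was not simulated. The direction holds under the common-SD model for any correlation, apart from the loss of one degree of freedom; the size does not.
- *The type I figure is hypothetical.* It requires someone to run both t-tests and keep the smaller p-value. Nothing in the documents says that the sponsor will do so, and the normality check does give a partial rule. The AIC-guided models were not simulated.
- *Further demands go too far.* A reader might also ask to drop the normality check, to allow one particular rank test as the only sensitivity analysis, or to add a statement on the Friedman test. The precision gain supports none of these.
- *The stakes are limited.* These are secondary endpoints in a Phase IV trial that seeks additional data, and the document calls itself a protocol summary. That lowers the rank but does not supply the missing choice.

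**Conclusion.** The point holds as a free improvement for secondary endpoints 1 and 3 only. The plan offers a list of methods, assigns none to TCSS or CAT, and commits to no baseline adjustment. Neither the t-test nor the two-visit repeated-measures ANOVA uses the collected baseline efficiently. They are valid tests, and the documents do not support calling them wrong or biased.

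With complete data, the power gain over the better t-test is about 1 to 11 points for TCSS, under the assumed means, SDs, correlations and true difference above. It is somewhat different with mean-filled values (3 to 13 points in the one setting checked). For CAT only the variance ratios 1−ρ² and (1+ρ)/2 can be given. The 8-10% type I error is a ceiling for a choice between two t-tests made after seeing results. It is not a forecast of the trial's conduct.

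**What to change.** For TCSS and CAT, pre-specify ANCOVA of the Week 4 score with treatment and the corresponding baseline score as the single main between-arm analysis in the Full Analysis Set. Use the same model for the Per protocol analysis already planned. Report the adjusted Rengalin-placebo difference with its 95% confidence interval. Any rank test is a sensitivity analysis only.

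The cost is a few lines of analysis-plan text. Both scores are already measured at both visits, and the GLM procedure (ANOVA, ANCOVA) is already listed. No new data, visits or patients are needed. The primary chi-square/Fisher test and the sample size of 95 per group (238 in total) stay as they are.
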